## 1 Introduction

The purpose of this Statistical Analysis Plan (SAP) is to describe the implementation of the statistical analysis for the following study:

CAIN457M2302 - A randomized, double-blind, multicenter study assessing short (16 weeks) and long-term efficacy (up to 1 year), safety, and tolerability of 2 subcutaneous secukinumab dose regimens in adult patients with moderate to severe hidradenitis suppurativa (SUNSHINE).

Data will be analyzed by Novartis according to the data analysis Section 12 of the study protocol which is available in Appendix 16.1.1 of the CSR. Important information is given in the following sections and details are provided, as applicable, in Appendix 16.1.9 of the CSR.

This document covers statistical and analytical plans for the final Week 52 analysis after all subjects have completed the study.

All analysis related to the primary and secondary objectives in the testing hierarchy are described in the Week 16 Primary Endpoint Analysis (PEA) SAP and are not covered in this final Week 52 SAP. The study and list of primary, secondary and exploratory objectives are kept for background.

### 1.1 Study design

This is a multicenter, randomized, double-blind, placebo controlled, parallel group study with two secukinumab dose regimens planned in approximately 541 subjects with moderate to severe hidradenitis suppurativa (HS).

The study consists of: Screening (up to 4 weeks), Treatment Period 1 (16 weeks) and Treatment Period 2 (36 weeks; optionally extended up to 48 weeks in case of pandemic major disruptions). Subjects who prematurely discontinue the study, or who complete the study and do not wish to continue in an optional extension study, will need to complete a post-treatment Follow-Up period (8 weeks).

Subjects will be randomized at a 1:1:0.5:0.5 ratio to one of four treatment arms at the time of randomization (baseline) visit:

- Secukinumab 300 mg every 2 weeks
- Secukinumab 300 mg every 4 weeks
- Placebo to secukinumab 300 mg every 2 weeks
- Placebo to secukinumab 300 mg every 4 weeks

Approximately 180 subjects are planned to be randomized to each of the two secukinumab arms and another approximately 180 subjects are planned to be randomized to the two placebo to secukinumab arms. Randomization will be stratified by region, current antibiotic use and body weight.

Subjects who complete Treatment Period 1 will enter Treatment Period 2. At Week 16, subjects who were randomized to one of the two secukinumab arms will continue on the same dose. Subjects who were randomized to the two placebo to secukinumab arms will start either

[figure not shown]
secukinumab 300 mg every 4 weeks or secukinumab 300 mg every 2 weeks according to their treatment arms definition.

The planned end of Treatment Period 2 visit (EOT 2) will be performed at Week 52. At this visit, the site should call Interactive Response Technology (IRT) after performing the scheduled study assessments to record the completion of the Treatment Period for the subject(s). For subjects rolling over to the optional extension study, Week 52 will be the end of study visit; for subjects continuing to the post-treatment Follow-Up period, the visit at Week 60 will be the end of study visit.

Subjects who discontinue study treatment prematurely for any reason other than withdrawal of informed consent before Week 52 should not be considered discontinued from the study. Subjects should continue attending site visits for the study assessments. Subjects who are unwilling to continue the further study visits after discontinuing the study drug should attend the end of study visit. The End of Treatment visit (EOT 1 for discontinuation during Treatment Period 1 and EOT 2 for discontinuation during Treatment Period 2) should be performed two weeks (where possible) after their last dose of study drug. After the EOT visit, subjects should enter the post-treatment Follow-Up period.

Only subjects who prematurely discontinue the study in Treatment Periods 1 or 2 for any reason, or subjects who do not enroll in the extension study will enter the post-treatment Follow-Up and potentially complete the Week 60 visit.

[figure not shown]
**Figure 1-1 Study design**

BSL: Baseline; EOT1/EOT2: End of Treatment 1/2; q2w: every two weeks; q4w: every four weeks. Treatment allocation for Placebo arm switching to secukinumab arms at Week 16 will be performed at the Randomization visit in 1:1 ratio and does not account for potential discontinuations during Treatment Period 1. Follow-Up: only subjects who prematurely discontinue treatment during Treatment Period 1 or 2 or subjects who do not enroll in the extension study, will enter Follow-Up.

In the event Week 52 cannot be performed on-site as scheduled due to a global health disruptive event, such as a pandemic/epidemic (e.g. COVID-19), or to a delay of HAs/ECs approval of the extension protocol, an additional treatment period of up to a maximum of 12 weeks (i.e., up to 6 doses, the frequency of study drug injections will remain every 2 weeks) could be considered to ensure therapeutic continuity for the patients until they are able to perform Week 52 visit onsite, and then participate in the long-term extension study.

**Figure 1-2 Study design in case of global health disruptive event.**

\*UNS = Unscheduled; UNS1, UNS2 and UNS3 correspond to three possible additional IRT calls at which 2 doses will be dispensed.

The primary endpoint will be evaluated at Week 16, which is the maximum acceptable duration of treatment exposure to placebo in this indication. The total study duration, including one year of treatment, will allow for assessment of long term safety and sustainability of the effect in the two secukinumab dose regimens.

A primary endpoint analysis (PEA) is planned after all subjects have completed the visit at Week 16 for regulatory submission. At the time of the primary endpoint analysis, the designated Novartis personnel (e.g. biostatisticians and programmers involved in the analysis, key Global Team members) may have access to the unblinded results. Field monitors/clinical research associates will remain blinded until final database lock. Subjects and site personnel directly involved in the conduct of the trial, i.e. investigator staff and persons performing the assessments, will remain blinded to individual treatment allocation until the conclusion of the study to ensure study integrity is maintained.

At the end of the study, a final analysis will be performed when all subjects have completed their last visit in the study and this is the focus of this SAP.

## 1.2 Study objectives, endpoints and estimands

describes the objectives and related endpoints

[figure not shown]
Table 1-1

[figure not shown]
**Table 1-1 Objective and related endpoints**

Objective(s)	Endpoint(s)
Primary objective(s)	Endpoint(s) for primary objective(s)

To demonstrate the efficacy of secukinumab compared to placebo with respect to HiSCR after 16 weeks of treatment.

	

Achievement of HiSCR at Week 16. HiSCR is defined as at least a 50% decrease in Abscess and Inflammatory Nodule (AN) count with no increase in the number of abscesses and/or in the number of draining fistulae.

Secondary objective(s)	Endpoint(s) for secondary objective(s)

To demonstrate the efficacy of secukinumab compared to placebo after 16 weeks of treatment with respect to AN count.

To demonstrate the efficacy of secukinumab compared to placebo with respect to:

proportion of subjects with HS flares

proportion of subjects with clinical response in HS related skin pain

	

Percentage change from baseline in AN count at Week 16.

Flaring up to Week 16. Flare is defined as at least a 25% increase in AN counts with a minimum increase of 2 AN relative to baseline.

Achievement of NRS30 at Week 16, among subjects with baseline NRS <math>\geq 3</math>.

Objective(s)	Endpoint(s)
	NRS30 is defined as at least a 30% reduction and at least 2 units reduction from baseline in Patient's Global Assessment of Skin Pain - at worst.
Exploratory objective(s)	Endpoint(s) for exploratory objective(s)


To evaluate the safety and tolerability of secukinumab over 52 weeks of treatment.

To explore the long-term effect of secukinumab with respect to HiSCR, AN count, proportion of subjects with flares, HS related skin pain up to 52 weeks of treatment.

To evaluate the effect of secukinumab with respect to the following efficacy assessments:

Modified Hidradenitis Suppurativa Score (mHSS);

HS-Physician's Global Assessment (HS-PGA);

Dermatology Life Quality Index (DLQI);

Health Status Questionnaire (EQ-5D-3L);

Patient Global Impression of severity (PGI-s);

Patient Global Impression of change (PGI-c);

Work Productivity Activity Impairment (WPAI);

HS Symptom Diary

Inflammatory markers with respect to CRP and ESR compared to placebo after 16 weeks and in the two secukinumab dose regimens up to 52 weeks of treatment.

	

Clinical safety and tolerability assessments:

physical exams,

vital signs,

laboratory assessments,

AE monitoring

Achievement of clinical response as defined by HiSCR, HiSCR25, HiSCR50, HiSCR75, HiSCR90, HiSCR100.

Absolute/percent and percentage change from baseline in AN count, AN (0/1), AN25, AN 50, AN75, AN90, AN100 response.

Flares.

Achievement of pain relief as defined by NRS30.

Absolute and percent change from baseline in modified Hidradenitis Suppurativa Score (mHSS).

HS-PGA response. HS-PGA response is defined as the achievement of at least a 2-point reduction in HS-PGA score compared to baseline.

DLQI response and absolute/percent DLQI total score change from baseline. DLQI response is defined as a decrease greater than 5.0 points from baseline in DLQI total score.

EQ-5D-3L Categories on Category questions and summary statistics on EQ - 5D -3L score questions.

Patient Global Impression of severity and change (PGI-s and PGI-c) categories.

Absolute and percent change from baseline in Work Productivity and Activity Impairment - Specific Health Problem (WPAI-SHP).

HS Symptom Diary items score change from baseline.

Objective(s)	Endpoint(s)


• To evaluate the pharmacokinetics of secukinumab in HS subjects.

• To assess the development of immunogenicity against secukinumab.

• To explore the potential association of biomarker levels with secukinumab efficacy and safety by visit up to Week 52 (EOT2).

• To explore the efficacy of secukinumab compared to placebo with respect to HiSCR response after 16 weeks of treatment, and the sustained efficacy over time in bio-naïve patients.

• To explore the efficacy of secukinumab compared to placebo with respect to HiSCR response after 16 weeks of treatment and the sustained efficacy over time in patients with body weight lower and higher than 90 kg (<90 kg and ≥90 kg).

	

• Absolute and percent change from baseline in CRP and ESR.

• AIN457 levels in serum

• anti-AIN457 antibodies levels in serum

• Biomarkers in serum

• Achievement of HiSCR at Week 16 and up to Week 52 in bio-naïve patients.

• Achievement of HiSCR at Week 16 and up to Week 52 in patients with body weight lower and higher than 90 kg (<90kg and ≥90kg).

### **1.2.1 Estimand**

The estimand framework relating to the primary and secondary estimands are described in the Week 16 PEA SAP.

## **2 Statistical methods**

### **2.1 Data analysis general information**

Novartis will be performing the analysis. Statistical software SAS version 9.4 or later will be used.

Summary statistics for continuous variables will include N, mean, standard deviation, minimum, lower quartile, median, upper quartile, maximum. Summary statistics for discrete variables will be presented in contingency tables and will include absolute and relative frequencies. Unless otherwise stated, summary tables/figures/listings will be based on all subjects included in the population under consideration.

Listings will be presented by treatment arms.

Footnotes will generally be provided for:

- abbreviations used in the output; abbreviations used on several outputs, e.g. for listings in Appendix 16.2 can be presented on a separate page and do not have to be repeated as footnotes on each listing
- sorting order of categories, e.g. for sorting within MedDRA (Medical Dictionary for Regulatory Activities) hierarchy levels
- MedDRA version used for reporting of MedDRA coded data

Footnotes will generally NOT be given for

- units displayed on the output

- interpretation of results (e.g., “odds ratio larger 1 favors active treatment”)
- information that can be retrieved from the statistical section of the clinical study report (CSR) unless it is not identifiable from the output, e.g.
  - explanation of analysis model used unless results of more than one model are displayed in an output
  - derivations of variables (e.g. BMI will not be explained in a footnote)
- information that will be provided in the clinical study protocol and/or methods section of the CSR (e.g. baseline definition if this is specified in the statistical section of the CSR)

### **2.1.1 Study Day 1 and other study days**

Day 1 is the day of the first drug administration of the study treatment (or randomization day if there has been no drug administration).

All other study days will be labeled relative to Day 1. For event dates on or after Day 1, study day for an event date is calculated as Date of event – [Day 1] + 1, i.e., Day 2, Day 3, etc., will be one day, two days, etc., after Day 1, respectively. For event dates before Day 1, study day for an event date is calculated as Date of event – [Day 1], i.e., Day -1, Day -2, etc., will be one day, two days, etc., before Day 1, respectively. Duration of an event will be calculated as (Event end date – Event start date + 1).

The descriptor “Day 0” will not be used.

### **2.1.2 Screening, baseline and post-baseline definitions**

*Screening* refers to any procedures (e.g., checking inclusion and exclusion criteria) performed prior to the first dose of study treatment. Per protocol, subject informed consent must be obtained prior to performing any study related activity. The date of signing informed consent is the start date of screening period. Any assessment obtained during the screening period will be labeled screening assessment. Assessments made on Day 1 may occur before or after the first dose.

### **Baseline definitions**

For efficacy analyses,

- For HS Symptom Diary assessment and Patient’s Global assessment of Skin Pain, the average of the latest 7 assessments before the date of the first drug administration of the study treatment (or randomization date if there has been no drug administration) will be used as baseline. In case less than 4 diary entries prior to the first dose of the study treatment were available, baseline will be set to missing.
- For all other efficacy assessments, baseline is the last assessment (including unscheduled visits) obtained (on or) before the day of the first drug administration of the study treatment (or randomization date if there has been no drug administration).

All assessments obtained after first dose (day) of study treatment are considered as post-baseline unless otherwise specified.

For safety analyses, baseline is the last assessment (including unscheduled visits) obtained (on or) before the first dose (day) of study treatment. All assessments obtained after the first dose (day) of study treatment are considered as post-baseline unless otherwise specified.

Of note, baseline will be derived based on first dose day, exact dosing time is not considered.

### **2.1.3 Day of last dose of study treatment**

The date of last dose will be collected via the CRF.

The subject's exposure will be calculated considering the last visit or the last dose + 84 days whichever occurs earlier.

## **2.2 Analysis sets**

The following analysis sets will be used for the data analysis.

The **Randomized Analysis Set (RAN)** consists of all randomized subjects. Subjects will be analyzed according to the treatment they are assigned to at randomization. Unless otherwise specified, misrandomized patients (mis-randomized in IRT) are excluded from the randomized set.

Mis-randomized patients are patients who were screen-failures, but had been randomized by the investigator before eligibility was finally assessed, however had not been treated.

Furthermore, all subjects with serious GCP violation at their site will be excluded from the randomized set.

The **Full Analysis Set (FAS)** consists of all subjects to whom study treatment has been assigned. Subjects will be analyzed according to the treatment assigned to at randomization. Mis-randomized subjects (mis-randomized in IRT) and subjects with serious GCP violation at their site will be excluded from FAS. If the actual stratum is different to the assigned stratum in IRT, the actual stratum will be used in analyses.

The **Safety Set (SAF)** includes all subjects who received at least one dose of study treatment. Subjects will be analyzed according to the study treatment received. Treatment received is defined as the randomized/assigned treatment if the subject took at least one dose of that treatment or the first treatment received if the randomized/assigned treatment was never received (subject received the wrong treatment during the entire study). Mis-randomized subjects and subjects with serious GCP violation at their site will be excluded from the safety set.

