12.1 Analysis sets

The Randomized Analysis Set (RAS) consists of all randomized subjects. Subjects will be analyzed according to the treatment assigned to at randomization.

The Full Analysis Set (FAS) comprises all subjects to whom study treatment has been assigned. Subjects will be analyzed according to the treatment assigned to at randomization. Mis-randomized subjects (mis-randomized in IRT) will be excluded from FAS. Mis-randomized subjects are defined as cases where IRT contacts were made by the site either prematurely or inappropriately prior to confirmation of the subject's final randomization eligibility and no study medication was administered to the subject.

The Safety Set includes all subjects who received at least one dose of study treatment. Subjects will be analyzed according to the study treatment received, where treatment received is defined as the randomized/assigned treatment if the patient took at least one dose of that treatment or the first treatment received if the randomized/assigned treatment was never received.

For all analysis in Treatment Period 1, the Placebo group to secukinumab 300 mg every 2 weeks and Placebo group to secukinumab 300 mg every 4 weeks will be pooled together.

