## 4 Change to protocol specified analyses

Response of HS-PGA is defined as the achievement of at least a 2-point reduction in HS-PGA score compared to baseline or the achievement of a “mild” status (defined as achieving an HS-PGA score of  $\leq 2$ ). While in the Protocol it is defined as at least a 2-point reduction in HS-PGA score only.

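### The Week 52 SAP removes dosed subjects at sites with a serious GCP violation from the Safety Set, contrary to the protocol, and does not list this in its Section 4

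*SAP*

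**What the plan says.** Protocol Section 12.1 defines the Safety Set in one step: "The Safety Set includes all subjects who received at least one dose of study treatment". The only exclusion in that section concerns the FAS: "Mis-randomized subjects (mis-randomized in IRT) will be excluded from FAS". The protocol's definition of such a subject includes that "no study medication was administered to the subject". The protocol has no exclusion by site or by GCP finding in any set.

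SAP Section 2.2 opens its Safety Set paragraph with the same all-dosed definition and closes it with "Mis-randomized subjects and subjects with serious GCP violation at their site will be excluded from the safety set". The same site clause appears for the randomized set ("Furthermore, all subjects with serious GCP violation at their site will be excluded from the randomized set") and for the FAS ("Mis-randomized subjects (mis-randomized in IRT) and subjects with serious GCP violation at their site will be excluded from FAS").

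SAP Table 5-2 puts the rule into operation. Two deviation codes, INCL01 and M-OTH07, exclude a subject from all three sets, and a subject outside the randomized set is also outside the Safety Set. A footnote ties INCL01 to written informed consent. M-OTH07 is not explained; it is presumably the GCP code.

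SAP Section 1 states that the analysis follows Section 12 of the protocol. SAP Section 4 names one change, the HS-PGA response definition: "While in the Protocol it is defined as at least a 2-point reduction in HS-PGA score only".

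**The concern.** A Safety Set exists to account for everyone exposed. SAP Section 2.6 bases all safety analyses on it, and Section 2.6.1 bases the ClinicalTrials.gov and EudraCT tables on it too. A dosed subject removed from the set takes any adverse event, SAE or death out of those outputs. Doubt about how a site counted lesions or kept its records is no reason to leave a death there uncounted.

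Nothing else in the SAP makes up for this. By default, outputs cover only the population under consideration (Section 2.1). Disposition uses the randomized set, from which the same subjects are removed. The Week 52 versus Week 16 reconciliation in Section 2.14 does not ask for subjects dropped from an analysis set. A reader of the report who relied on the protocol definition would take the denominators to be all dosed subjects, and Section 4 would not correct that.

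**Working it through.** The plan gives no figure for this point, so the check is mainly a comparison of text.

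**1. Definitions side by side**

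| Set | Protocol 12.1 | SAP 2.2 and Table 5-2 | Can the SAP rule remove a dosed subject? |
|---|---|---|---|
| Randomized | "The Randomized Analysis Set (RAS) consists of all randomized subjects" | Also drops mis-randomized subjects (unless otherwise specified), GCP-violation sites, INCL01 and M-OTH07 | Yes |
| FAS | Drops mis-randomized subjects only | Also drops GCP-violation sites, INCL01 and M-OTH07 | Yes |
| Safety | All dosed subjects | All dosed subjects, then minus GCP-violation sites, INCL01, M-OTH07 and anyone outside the randomized set | Yes |

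**2. Which part of the closing sentence matters.** Both documents define mis-randomized subjects as untreated. They could never enter a set of dosed subjects, so that half of the sentence changes nothing in the Safety Set. The site half has no such limit and reaches dosed subjects.

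**3. Internal consistency.** The SAP paragraph first includes every dosed subject and then removes some. Both statements hold only if no dosed subject was at an affected site.

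**4. Declaration.** Section 4 has one entry, on HS-PGA. The document-history table is empty. Within this SAP, the departure is therefore not listed as a change.

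**5. Size.** The protocol summary gives approximately 541 subjects at approximately 132 sites.

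- Average site: 541/132 = 4.1 subjects.
- Share of the sample: 4.1/541 = 0.76%, about 0.8%.
- The number actually excluded is not in the documents. If it were 4 to 40 subjects (an assumption), the share would be 4/541 = 0.7% to 40/541 = 7.4%.

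**6. Effect on a rare event (illustration; the counts are assumed).** Take an arm of 180 in which 4 subjects have a given event. Remove 4 subjects from that arm, one of whom had the event. The rate goes from 4/180 = 2.2% to 3/176 = 1.7%. An average site's patients would usually be spread over several arms, so this shows the mechanism and does not forecast a result.

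**The case against.** Several points on the other side are sound.

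- **Scope.** This SAP covers only the final Week 52 analysis. The Week 16 primary endpoint SAP, which was not available, may define and justify the same sets. What can be shown is absence from Section 4 of this SAP, not absence everywhere.
- **Openness.** The rule is stated plainly for each set and implemented in a table. It is not hidden.
- **Site level.** The clause turns on the site, not on a subject's arm or outcome. It removes whichever arms are present there and is less prone to bias than selecting individual subjects.
- **Unreliable data.** If a site under-reported events, pooling it could dilute the adverse event rates. That supports showing results both ways; it does not support leaving exposed subjects out altogether.
- **Oversight.** SAEs must still reach the sponsor's safety group within 24 hours whatever the causality (protocol Section 10.1.3), and a DMC assesses safety data (Section 10.2.1). The events stay under review, but neither channel supplies complete rates in the report.
- **Consent.** Read literally, an all-dosed set would bring back INCL01 subjects, whose data it may not be permissible to use. The fix has to allow for that.

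A reader might infer that the sponsor could trim the FAS after seeing Week 16 results, or that the primary result is at risk. The documents do not support this. Designated staff may see unblinded Week 16 results (SAP Section 1.1), but nothing says that the criterion was set or would be applied after that. The confirmatory tests are outside this SAP, and its efficacy models are exploratory and use observed data. What remains is a gap in documentation: the SAP does not define a serious GCP violation, say who decides, or say when.

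**Conclusion.** The conflict over the Safety Set is real. Applied as written, the SAP would leave dosed subjects at an affected site out of all safety summaries and registry tables, against protocol Section 12.1 and against the SAP's own opening definition. Section 4 of this SAP does not list the change.

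The practical size is unknown and may be zero, because no document shows that any site had a serious GCP violation. One average site is about 4.1 subjects, or 0.8% of the sample; anything larger is an assumption. What is at stake is complete safety counts.

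Whether to drop such a site from the exploratory Week 52 efficacy analyses is a judgement call and is not part of the error. The randomized-set and FAS exclusions need only be declared. The conclusion rests on the protocol and the Week 52 SAP alone; a declaration in the Week 16 SAP would narrow the point about disclosure but would not remove the conflict with the protocol's Safety Set.

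**What to change.** 1. In SAP Section 2.2 and Table 5-2, restore the protocol Safety Set: all dosed subjects, except where lack of valid consent (INCL01) bars use of the data.
2. If a site's data are judged unreliable, present safety with and without that site. At the least, list the excluded subjects with their exposure, adverse events, SAEs and deaths.
3. Define a serious GCP violation, explain M-OTH07, name who decides, and fix the site criterion blind to treatment.
4. Declare every departure from protocol Section 12.1 that is kept, including the randomized-set and FAS exclusions, in SAP Section 4 with a reason.

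The cost is SAP wording. Extra safety tables or a listing are needed only if such a site exists.
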